2.6 Timing of Final Analysis

A maximum number of 700 patients will be enrolled. The study may be stopped earlier due to futility (non-binding criterion) or success (binding criterion) after interim analyses with about 200 patients, 350 patients, 550 patients and 650 patients (see previous section for more information). In any case the final analysis will be conducted comprising all patients enrolled into the study until the implementation of study stop. The final analysis will be conducted with complete 30 day follow-up data of all enrolled patients.

3 Study Population

Hospitalized adult patients with suspected or confirmed pneumonia at time of admission or while admitted to the ED who are prescribed antibiotics (including septic patients with respiratory focus) are enrolled into the study. Please refer to the study protocol for additional medical information, e.g. concerning eligibility criteria (inclusion and exclusion criteria in Section 4.2.1 and 4.2.2 of the protocol, respectively).

3.1 Analysis Populations

The intention-to-treat (“ITT”) patient population will comprise all randomized non-COVID-19 patients. The per-protocol (“PP”) patient population will comprise all ITT patients (a) fulfilling study inclusion criteria, (b) not meeting study exclusion criteria at enrollment, (c) even if meeting study exclusion criterion after enrollment or meeting a pre-defined overruling criterion, (d) with PCT measurements performed daily in the first week and thereafter at least every 48 hours during antibiotic treatment, (e) ~~-if assigned to PCT group, antibiotic steward~~ ship team recommendation given to the treating physician on enrollment day and for each PCT measurement taken Monday-Friday described under d) and antibiotics stopped according to the PCT algorithm. An exception will be made if the ASP decides the patient will be given the same recommendation throughout their hospitalization.

Consequently, it should be noted that ASP recommendations should also be provided for patients meeting pre-defined overruling criteria (e.g., need for ICU care) since such patients may still qualify for the per-protocol population.

Patients of the PCT arm who are discharged before that day’s PCT has resulted will be excluded from the per protocol population. Patients in the PCT arm who were continued on antibiotics despite a weekend/holiday/no ASP member available PCT value that would have resulted in an ASP recommendation to stop antibiotics will also be excluded from the per protocol population. Patients in the PCT arm whose antibiotics were discontinued despite weekend/holiday/no ASP member available PCT value that would have resulted in continuation of antibiotics will also be excluded.

(f) if assigned to control group, no PCT measurements to treating physician during index hospitalization.

Primary analysis of the superiority endpoint “antibiotic exposure” will be conducted on the basis of the ITT patient population. Analysis of the non-inferiority endpoint “composite adverse events until

day 30" will be conducted on the basis of PP and ITT patient population. PP-results will be compared and discussed with corresponding results obtained for ITT patient population.

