1.6 Study Plan

	Between presentation and enrollment day	Screening/ Enrollment day	Per Protocol until discharge (as available)	Hospital Discharge	Day 30
Medical History	x				
Routine Clinical Assessment	x	x	x		
Standard laboratory evaluation	x	x	x		
Inclusion/Exclusion		x			
PCT measurement	x	x	x*		
Document presence or absence of safety endpoints and antibiotic prescription				x	x
Follow-up via chart review/public record: readmission, survival status					x
Follow-up via chart review: Readmission for CDI					x

*PCT measurement only until antibiotics are stopped or patient becomes ineligible

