Upon randomization, the research staff will send a welcome message to both the standard of care and intervention teams. Enrollment PCT values consist of one value from the day of randomization (D1) and one value from a previous day 6-48 hours prior (D0). All PCT measurements throughout the study should be obtained using discarded blood from routine lab work. All PCT values ordered by the study team for patients in the intervention arm will be released in EPIC, while those of the standard of care arm will be suppressed.

After the PCT results are available, the stewardship team will review both the D0 and D1 results as a pair and provide an antibiotic recommendation (PCT intervention arm only) using the stewardship team recommendation template to the primary provider service on enrollment day. If the stewardship team is discordant with the PCT algorithm (see section 1.5 for algorithm), they will be sent a discordance survey (see Appendix G). If the primary team is discordant with the stewardship recommendations, a reason for discordance survey will be sent out and recorded in REDCap (see Appendix H). Patient information will be recorded in REDCap for both the intervention and standard of care arms.

(D2+) Daily PCT measurements

For patients who are still eligible and on antibiotics, PCT should be measured daily for one week and then Monday, Wednesday, and Friday in both arms. If there are no results on a Monday, the PCT will be measured on Tuesday, Wednesday, and Friday. If there are no results on a Wednesday, the PCT will be measured on Monday, Thursday, and Friday.

For PCT arm patients, the stewardship team will review available PCT results and provide an antibiotic recommendation to the primary provider service on the same calendar day. Antibiotic monitoring and/or discontinuation will be guided by clinical assessment (medical history, physical exam, imaging and standard laboratory evaluations) as well as the PCT algorithm (Appendix A, LRTI) and pre-defined overruling criteria (Appendix A, 11.2). If the stewardship team is discordant with the PCT algorithm, a discordance survey will be requested (Appendix G). In case of discordance between the primary team and the stewardship team, a discordance survey will also be requested (Appendix H).

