8.4 Analysis Populations

The intention-to-treat (“**ITT**”) patient population will comprise all randomized non-COVID-19 patients.

The per-protocol (“**PP**”) patient population will comprise all ITT patients

- (a) fulfilling study inclusion criteria,
- (b) not meeting study exclusion criteria at enrollment,
- (c) even if meeting study exclusion criterion after enrollment or meeting a pre-defined overruling criterion,

- (d) with PCT measurements performed daily in the first week and thereafter at least every 48 hours during hospitalization and antibiotic treatment,
- (e) if assigned to PCT group, antibiotic steward ship team recommendation given to the treating physician on enrollment day and for each PCT measurement taken Monday-Friday described under d) and antibiotics stopped according to the PCT algorithm. An exception will be made if the stewardship team decides the patient will be given the same recommendation throughout their hospitalization.

Consequently, it should be noted that stewardship team recommendations should also be provided for patients meeting pre-defined overruling criteria (e.g., need for ICU care) since such patients may still qualify for the per-protocol population.

Patients of the PCT arm who are discharged before that day's PCT has resulted will be excluded from the per protocol population. Patients in the PCT arm who were continued on antibiotics despite a weekend/holiday/no stewardship team member available PCT value that would have resulted in an stewardship team recommendation to stop antibiotics will also be excluded from the per protocol population. Patients in the PCT arm whose antibiotics were discontinued despite weekend/holiday/no stewardship team member available PCT value that would have resulted in continuation of antibiotics will also be excluded.

- (f) if assigned to control group, no PCT measurements to treating physician during index hospitalization.

Primary analysis of the superiority endpoint “antibiotic exposure” will be conducted on the basis of the ITT patient population. Analysis of the non-inferiority endpoint “composite adverse events until day 30” will be conducted on the basis of PP and ITT patient population. PP-results will be compared and discussed with corresponding results obtained for ITT patient population.

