8.6.3 Secondary Analysis of CAE30

The first secondary endpoint “composite adverse events until day 30” (CAE30) will be analyzed for safety non-inferiority of the PCT arm vs. the control arm on the basis of the PP patient population. The analysis will also be conducted on the basis of the ITT patient populations and ITT- and PP-results will be compared and discussed. Differences in proportions of CAE30 between PCT arm and control arm will be assessed by Bayesian analysis assuming binomially distributed events (beta-distributed study-arm specific CAE30 probabilities) and uninformative uniform priors. More specifically, the following generative model will be used:

$$NE_{PCT} \sim \text{Binomial}(N_{PCT}, p_{PCT})$$

$$NE_{ctrl} \sim \text{Binomial}(N_{ctrl}, p_{ctrl})$$

$p_{PCT}, p_{ctrl} \sim \text{Uniform}(0, 1)$

with

NE_{PCT}, NE_{ctrl} : number of patients with CAE30 of the PCT arm and control arm, respectively

N_{PCT}, N_{ctrl} : number of patients randomized to the PCT arm and control arm, respectively

p_{PCT}, p_{ctrl} : CAE30 probability for patients of the PCT arm and control arm, respectively

Differences between study-arm specific CAE30 probabilities will be computed by Monte Carlo simulation sampling CAE30 probabilities p_{PCT}, p_{ctrl} from their analytically computed study-arm specific posterior probabilities. Study success is specified by more than 98.5%¹ posterior probability for a CAE30 probability of patients of the PCT arm smaller than the CAE30 probability of patients of the control arm plus 10% (NI margin):

Probability(CAE30 probability of PCT arm < CAE30 probability of control arm + 10%) > 98.5% ¹,

or with the above introduced notation

Probability($p_{PCT} < p_{ctrl} + 0.1$) > 98.5% ¹.

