4.5 Secondary Analysis of CAE30

The first secondary endpoint “composite adverse events until day 30” (CAE30) will be analyzed for safety non-inferiority of the PCT arm vs. the Control arm on the basis of the PP patient population. The analysis will also be conducted on the basis of the ITT patient populations and ITT- and PP-results will be compared and discussed. Differences in proportions of CAE30 between PCT arm and Control arm will be assessed by Bayesian analysis assuming binomially distributed events. Posterior probabilities will be computed study-arm specifically using conjugate beta-distributed and

uninformative uniform priors (shape parameters $\alpha = \beta = 1$). More specifically, the following generative model will be used:

$$\begin{aligned} NE_{PCT} &\sim \text{Binomial}(N_{PCT}, p_{PCT}) \\ NE_{ctrl} &\sim \text{Binomial}(N_{ctrl}, p_{ctrl}) \\ \text{priors: } p_{PCT}, p_{ctrl} &\sim \text{Uniform}(0, 1) \end{aligned}$$

with

NE_{PCT}, NE_{ctrl} : number of patients with CAE30 of the PCT arm and Control arm, respectively

N_{PCT}, N_{ctrl} : number of patients randomized to the PCT arm and Control arm, respectively

p_{PCT}, p_{ctrl} : CAE30 probability for patients of the PCT arm and Control arm, respectively

Differences between beta-distributed study-arm specific CAE30 posterior probabilities will be computed by Monte Carlo simulation sampling CAE30 probabilities p_{PCT}, p_{ctrl} from their analytically computed study-arm specific posterior probabilities. Study success is specified by more than $\gamma = 0.985$ posterior probability for a CAE30 probability of patients of the PCT arm smaller than the CAE30 probability of the Control arm plus $M = 10\%$ (NI margin):

$$\text{Probability(CAE30 probability of PCT arm} < \text{CAE30 probability of Control arm} + M \text{)} > \gamma ,$$

or with the above introduced notation

$$\text{Probability(} p_{PCT} < p_{ctrl} + M \text{)} > \gamma .$$

See Section 2.3 for the computation of the parameter γ which was set to $\gamma = 0.985$.

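### Per-protocol criterion (d) allows 48 hours between PCT measurements after week one, but the protocol's own schedule leaves 72 to 96 hours, so adherent patients can fall out of the set used for CAE30 non-inferiority

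*SAP*

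**What the plan says.** - **Schedule (Protocol 4.1).** For eligible patients on antibiotics, "PCT should be measured daily for one week and then Monday, Wednesday, and Friday in both arms". Two fallbacks follow: "If there are no results on a Monday, the PCT will be measured on Tuesday, Wednesday, and Friday" and "If there are no results on a Wednesday, the PCT will be measured on Monday, Thursday, and Friday". The Protocol 1.6 table adds: "PCT measurement only until antibiotics are stopped or patient becomes ineligible".
- **PP criterion (d).** The protocol (8.4) asks for patients "with PCT measurements performed daily in the first week and thereafter at least every 48 hours during hospitalization and antibiotic treatment". The SAP (3.1) asks for patients "with PCT measurements performed daily in the first week and thereafter at least every 48 hours during antibiotic treatment", dropping the restriction to the hospital stay.
- **Use of the PP set.** CAE30 "will be analyzed for safety non-inferiority of the PCT arm vs. the control arm on the basis of the PP patient population" (Protocol 8.6.3; SAP 4.5 says the same), with ITT run alongside. SAP 2.3.3 simulated the CAE30 test on PP, taken as a random 50% of patients. SAP 2.4 makes CAE30 non-inferiority the gate to prescribedABx. Protocol 8.4 and SAP 3.1 themselves name both PP and ITT for this endpoint.

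**The concern.** The population rule and the sampling schedule cannot both be met by a patient who stays in hospital on antibiotics across a weekend after the daily week. The weekend and holiday sentences in Protocol 8.4 and SAP 3.1 do not resolve this. They cover stewardship recommendations and stop or continue decisions in the PCT arm. They do not relax the sampling interval, and they do not help the control arm, to which (d) also applies.

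Whether a patient is still on antibiotics in week two is decided after randomization, and it is what the intervention aims to change. Removing adherent patients on that basis is not the random 50% subset that SAP 2.3.3 assumes. Two analysts, one reading (d) literally and one reading it as adherence to schedule, would build different PP sets for a safety conclusion.

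The missing hospital restriction in the SAP is a second wording fault. Read literally, it would require PCT during antibiotics taken after discharge. The pilot PP set kept patients discharged on antibiotics (7/30 PCT, 19/29 control; Protocol Table 8.1), so that reading was evidently not used there.

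**Working it through.** **1. The plan's own figure.** SAP 2.3.3 gives 75% power for CAE30 non-inferiority. Inputs: marginal rate 20%, RR 0.9, margin 0.10, threshold 0.985, and 50% of 700 in PP, so 175 per arm.

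- Control rate = 0.40/1.9 = 0.2105; PCT rate = 0.9 × 0.2105 = 0.1895.
- SE = √[(0.2105 × 0.7895 + 0.1895 × 0.8105)/175] = 0.0427.
- Power = Φ[(0.10 + 0.0211)/0.0427 − 2.170] = Φ(0.66) = 74.6%.
- Simulating the beta-binomial rule at a fixed 175 per arm gives about 75%. The figure reproduces.

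**2. Intervals in the Protocol 4.1 schedule after the daily week**

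| Pattern | Intervals | Longest |
|---|---|---|
| Mon/Wed/Fri | 48, 48, then 72 h (Fri–Mon) | 72 h |
| No Monday result: Tue/Wed/Fri | 96 h (Fri–Tue), 24, 48 | 96 h |
| No Wednesday result: Mon/Thu/Fri | 72 h (Mon–Thu), 24, 72 (Fri–Mon) | 72 h |

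Criterion (d) allows 48 h. Every pattern exceeds it at least once a week.

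**3. Day on which the first gap over 48 h ends** (regular schedule, day 1 = enrolment)

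| Daily week | Mon | Tue | Wed | Thu | Fri | Sat | Sun |
|---|---|---|---|---|---|---|---|
| Days 1–7 | 15 | 14 | 13 | 12 | 11 | 10 | 16 |
| Days 2–8 | 15 | 14 | 13 | 12 | 11 | 17 | 16 |

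Columns are enrolment weekdays. A patient in hospital and on antibiotics on that day fails (d) with every scheduled PCT done.

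**4. Upper bound on the share.** Assume antibiotics run through the whole stay, and use the SAP 2.3.2 stay distribution (exponential, rate 0.12; per day is my assumption, as no unit is given). Averaging exp(−0.12 × day) over the days 1–7 row gives (0.165 + 0.186 + 0.210 + 0.237 + 0.267 + 0.301 + 0.147)/7 = 21.6%. Counting part-days as whole days multiplies this by exp(0.12), giving 24.4%.

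**5. Illustrative shares.** The last in-hospital antibiotic day is taken as the smaller of stay and antibiotic duration, drawn independently. Durations are fitted (normal, gamma, lognormal) to the medians and quartiles in Protocol Appendix E: control 10 (7, 12), PCT 7 (4, 10). A second setting scales them by 0.7 and 0.9 towards the pilot's short-course rates, which is a crude assumption. There were 1,000,000 simulated patients per setting.

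| Failing (d), daily week days 1–7 | Control | PCT |
|---|---|---|
| Appendix E durations | 5.9–8.5% | 2.8–5.5% |
| Scaled durations | 0.9–2.7% | 1.7–4.5% |
| Appendix E, correlation 0.5 | 10.7–14.1% | 6.0–10.5% |
| Scaled, correlation 0.5 | 2.1–5.7% | 4.1–9.0% |

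The arm difference reverses between settings. Neither setting fits the pilot ITT data in both arms:

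- Unscaled: 0.4–5% short courses in control, against 5/47 (11%).
- Scaled: control fits (4–12% short; 49–57% discharged on antibiotics, against 24/46, 52%). The PCT arm has 19–28% short, against 14/48 (29%), but 43–54% discharged on antibiotics, against 15/47 (32%).

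None of these shares is offered as an estimate.

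**6. Power if these losses are additional** (fixed sample, Bayesian rule)

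| PP patients, PCT / control | Power |
|---|---|
| 175 / 175 | 74.9% |
| 171 / 173 | 74.1% |
| 168 / 168 | 73.0% |
| 167 / 162 | 72.3% |

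**7. Threshold.** SAP 2.3.3 calibrated 0.985 with RR for CAE30 of 0.30 (control 0.40/1.3 = 30.8%, PCT 9.2%). Non-inferiority then succeeds 99.99% of the time at 100 per arm and 100% at 175, so the PP share hardly affects that calibration.

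**The case against.** The case for treating this as minor has several parts.

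- **Criterion (d) may be meant as adherence to planned sampling.** Criterion (c) keeps patients who meet an exclusion after enrolment, yet Protocol 1.6 and 6.2 stop PCT in them, so a literal (d) would largely defeat (c). This is a fair guess at intent, but the text does not say it. SAP version 5 was issued partly to reduce ambiguity and left (d) as it was.
- **Some patients may be sampled more often.** Protocol 5.1 speaks of leftover serum from daily routine draws. That does not override the explicit Monday, Wednesday and Friday rule.
- **PP already drops blameless patients,** such as PCT-arm patients whose weekend value was not acted on. True for the PCT arm through (e). Criterion (d) adds an avoidable loss and reaches the control arm too.
- **The illustrative shares lean high.** This stands in part. With the daily week on days 2–8, the unscaled shares fall to about 3.5–7% (control) and 2–4% (PCT). Without whole-day rounding, the scaled shares are 0.3–1.2% and 1.0–2.7%. The models also ignore the exclusion of infections normally treated for more than two weeks.
- **The power loss may be nil.** The 50% PP share was estimated from the running study, so losses under (d) may already be in it. The documents do not say.
- **ITT is also run for CAE30.** This is a real safeguard, but the simulated hierarchy uses PP.

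**Conclusion.** The contradiction is certain: it follows from the calendar alone and appears in both documents. As written, (d) excludes some patients whose PCT was measured exactly as the protocol asks, from the population on which CAE30 non-inferiority is tested.

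The consequence is probably modest and cannot be sized from the documents. Under independent stay and duration the illustrative shares run from under 1% to about 9% per arm. They are higher if stay and duration are correlated, and 22–24% is the ceiling if antibiotics last the whole stay (daily week on days 1–7). All of this rests on a per-day reading of the stay rate and on borrowed duration data. I claim no direction of bias.

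The CAE30 power loss is about 1 to 3 points if the exclusions are additional to the 50% PP share, and zero if they are already in it. The primary ITT analysis is unaffected and the 0.985 threshold is not materially affected. It should be fixed because it concerns a safety conclusion and costs almost nothing.

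**What to change.** Reconcile Protocol 4.1, Protocol 8.4 and SAP 3.1 before PP membership is fixed and without reference to unblinded outcomes:

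1. Define (d), in identical words in both documents, as adherence to the Protocol 4.1 PCT schedule, including its fallback days, while the patient is in hospital and on antibiotics. This also closes the post-discharge reading of the SAP.
2. State whether the 50% PP estimate applied (d) literally. If the PP share changes, restate the 75% CAE30 power.

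The cost is one sentence per document, with no new data. Because the 350-patient interim analysis has already taken place (SAP version history), the change needs a dated, documented rationale. No view is taken on what the sampling schedule should be.

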4.2.2 Exclusion Criteria

- Patient has tested positive for SARS-CoV-2
- Patients who are not admitted to the hospital
- Patients admitted to home health
- Major surgeries, defined as any procedure in which an incision is made with the exception of superficial procedures (eyes, cornea, skin, dental procedures), organs removed, or normal anatomy altered (e.g. open thoracic, abdominal and/or major orthopedic surgery), in the past 1 month or expected surgical procedure or patient receiving antibiotics for surgical prophylaxis
- Known Pregnancy
- Primary and acquired cell-mediated immune deficiency (HIV with CD4 <350 cells/mm³; with receipt of systemic chemotherapy and/or biologics in the past 3 months for reasons other than malignancy)
- Active metastatic cancer or neuroendocrine tumor or liquid tumor and/or on check point inhibitors within 3 months or has signs of mucositis (e.g. mouth lesions or intestinal bleeding).
- Neutropenia (<1,500 ANC)
- Patients with cystic fibrosis
- Infection where long courses of antibiotics are the standard of care (more than 2 weeks) other than for anti-inflammatory reasons
- Concomitant non-pulmonary bacterial infection that requires antibiotic therapy based on an active medical team decision.
- Antibiotics given for non-infectious indications (e.g. rifaximin for hepatic encephalopathy)
- Patients receiving dialysis
- Patients with solid organ transplant, bone marrow transplant or stem cell transplant recipient
- ST elevation myocardial infarction
- Prior enrollment into this study within 30 days
- Patient experiencing major trauma defined as any injury that could cause prolonged disability and/or an Injury Severity Score >15, and/or burns or patient under extracorporeal circulation confirmed by a second research staff member.
- Patient with acute viral hepatitis and/or decompensated severe liver cirrhosis (Child-Pugh Class C).
- Patient with prolonged or severe cardiogenic shock defined as decreased cardiac output leading to end organ injury (e.g. severe hypotension or AKI or oliguria or altered mental status or cool extremities or respiratory distress AND evidence of metabolic acidosis on lab testing).
- Patient with pancreatitis, chemical pneumonitis or heat stroke
- Active infection with invasive fungal pathogen (e.g. candidiasis, aspergillosis) or plasmodium falciparum malaria or mycobacteria

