- Patient under treatment with OKT3 antibodies, OK-432, interleukins, TNF-alpha and other drugs stimulating the release of pro-inflammatory cytokines or resulting in anaphylaxis.
- Patient is under hospice care
- Patient with ventilator-associated pneumonia
- Patients with untreated, active, and symptomatic autoimmune disease
- Patients actively enrolled in other clinical trial involving immunomodulatory therapy.
- Patient with empyema, abscess, or cavitary/necrotizing pneumonia

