6.2 Procalcitonin (PCT) Measurement

Procalcitonin will be measured with the Elecsys B·R·A·H·M·S PCT™ assay or Abbott Alinity and site personnel will be responsible for PCT measurements according to standard hospital procedure.

PCT results will be unblinded in the PCT arm (i.e. antibiotic management guided by the PCT algorithm + stewardship team) and blinded in the control arm (i.e. antibiotic management guided by standard of care). Research staff will enter PCT results in the eCRF (REDCap) and also ensure that the stewardship team views the results and makes a recommendation for PCT arm patients at the time frames specified in section 4.1.

Every site will have an SOP or delegation log with all key personnel listed including the core lab director/manager who will have confirmed that their site has PCT testing validated and ready for use.

If during the hospital course, patients meet an enrollment ineligibility criterion (e.g., developed a non-pulmonary infection, had to undergo a major surgery...), PCT levels will stop being measured and no further intervention from the stewardship team will be made. However, patients will continue to be monitored.

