4.1.2 Composite adverse events until day 30 ("CAE30", first secondary endpoint)

will be encoded as the patient level Boolean inclusive disjunction ("OR") of the following eight binary (true/false) single adverse event endpoints (1a) all-cause in-hospital mortality, (1b) all-cause mortality after discharge (as available), (2) septic shock (vasopressor use for > 1 h), (3) mechanical ventilation (via endotracheal tube for respiratory failure), (4) needed dialysis, (5) lung abscess/empyema/cavitation/necrotizing pneumonia or (6) hospital readmission.

In the case a patient is enrolled with mechanical ventilation, such an event is not considered to be an adverse event due to its occurrence before any intervention. If the patient is then extubated during their hospital stay, re-intubation is only classified as an adverse event if it occurs at least 24 hours post extubation.

In the case a patient is enrolled with septic shock, such an event is not considered to be an adverse event due to its occurrence before any intervention. If the patient then has a resolved septic shock during hospital stay, developing a new septic shock is only classified as an adverse event if it occurs at least 24 hours post resolution of the initial septic shock.

In the case a patient develops a safety adverse event at any point on the day of enrollment post randomization, such an event will be classified as an adverse event.¹

The variable CAE30 mirrors the safety endpoint for pneumonia used in the study ProACT [Huang2018]. And, also as in ProACT, the endpoint will be analyzed in the form of study-arm-specific proportions, see Section 4.3ff.

4.1.3 Antibiotic exposure at discharge (“prescribedABx”, second secondary endpoint) will be encoded as the proportion of patients per study arm (PCT arm, control arm) with antibiotic prescription for pneumonia treatment at discharge from index hospitalization.

The numerical endpoint **antibiotic duration** is the third secondary endpoint, see definition in Section 4.1.1.

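### Dialysis and lung abscess/empyema are both CAE30 events and grounds for stopping PCT; read literally, PP criterion (d) then drops the patient, in conflict with criterion (c)

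*SAP*

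**What the plan says.** **PP membership.** SAP 3.1 lists conditions (a) to (f). Condition (d) admits patients "with PCT measurements performed daily in the first week and thereafter at least every 48 hours during antibiotic treatment". Protocol 8.4(d) is the same except that it also refers to hospitalization. Neither has an exception for PCT that the protocol itself has stopped. Condition (c), in the same list, keeps patients "even if meeting study exclusion criterion after enrollment or meeting a pre-defined overruling criterion".

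**When PCT stops.** Protocol 4.1 ties measurement to eligibility: "For patients who are still eligible and on antibiotics, PCT should be measured daily for one week". The footnote to the protocol 1.6 table says "PCT measurement only until antibiotics are stopped or patient becomes ineligible". Protocol 6.2 covers a patient who meets an ineligibility criterion during the stay: "PCT levels will stop being measured and no further intervention from the stewardship team will be made". Monitoring of the patient continues.

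**The overlap.** Protocol 4.2.2 excludes "Patients receiving dialysis" and "Patient with empyema, abscess, or cavitary/necrotizing pneumonia". SAP 4.1.2 counts the same conditions as CAE30 components: "4) needed dialysis, (5) lung abscess/empyema/cavitation/necrotizing pneumonia or (6) hospital readmission".

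**Use of PP.** SAP 4.5 tests CAE30 non-inferiority on PP and also runs the analysis on ITT for comparison. SAP 2.3.3 uses PP for the interim and final CAE30 analyses, and Table 2.6 makes PP the basis of the second step in the testing hierarchy.

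**The concern.** Take a patient, in either arm, who develops empyema on day 4. Protocol 6.2 ends PCT measurement. If antibiotics continue, the patient has treatment days without PCT and no longer satisfies the wording of (d). Nobody departed from the protocol; the patient leaves PP because the safety event happened. The same holds for a patient who starts dialysis while on antibiotics.

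Removing patients because they had the event lowers the observed CAE30 rate in both arms and shrinks the absolute difference, while the margin stays at 10 percentage points. That favours a non-inferiority conclusion. The effect is larger if any excess harm in the PCT arm falls in these components. It also breaks an assumption of the design work, which treated PP as a random half of all patients.

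**Working it through.** **1. Reproduce the plan's figure.** SAP 2.3.3 gives 75% power for CAE30 non-inferiority on PP. Its inputs are a marginal CAE30 rate of 20%, RR 0.9, margin 0.10, threshold 0.985, and PP as a random 50% of 700 (175 per arm).

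- Control rate = 0.40/1.9 = 21.05%; PCT rate = 0.9 × 21.05% = 18.95%.
- Success means P(p_PCT < p_ctrl + 0.10) > 0.985 with uniform Beta(1,1) priors. Exact summation over both binomials at 175 per arm gives 74.9%.
- An approximate adaptive simulation (20,000 trials, success looks at 550 and 650, hierarchical testing) gives 99% / 76% / 49% for shortABx / CAE30 / prescribedABx. The SAP states 99% / 75% / 48%.

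The stated power reproduces, with PP membership unrelated to outcome.

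**2. Put the truth at the margin.** Assume 30% in the PCT arm, 20% in control and 175 PP per arm. With every event kept, the same calculation gives a false non-inferiority rate of 1.6%.

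**3. Remove a share f of event patients from both arms.** The observed rate becomes p(1 − f)/(1 − pf). For example, at f = 0.2: 0.30 × 0.8/(1 − 0.06) = 25.5% and 0.20 × 0.8/(1 − 0.04) = 16.7%.

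| Share of events removed | PCT | Control | Difference (points) | False NI |
|---|---|---|---|---|
| 0% | 30.0% | 20.0% | 10.0 | 1.6% |
| 5% | 28.9% | 19.2% | 9.7 | 1.8% |
| 10% | 27.8% | 18.4% | 9.5 | 2.1% |
| 15% | 26.7% | 17.5% | 9.2 | 2.5% |
| 20% | 25.5% | 16.7% | 8.9 | 2.9% |
| 30% | 23.1% | 14.9% | 8.2 | 4.3% |

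**4. Remove unequal amounts.** If r points of an arm's patients are removed, all with events, the observed rate is (p − r)/(1 − r). For 5 v 2 points: (0.30 − 0.05)/0.95 = 26.3% and (0.20 − 0.02)/0.98 = 18.4%.

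| Points removed, PCT v control | Difference (points) | False NI |
|---|---|---|
| 2 v 1 | 9.4 | 2.2% |
| 3 v 1 | 8.6 | 3.2% |
| 5 v 2 | 8.0 | 4.6% |
| 7 v 2 | 6.4 | 9.3% |

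Both tables hold n at 175 per arm. Reducing n by the patients removed changes each entry by at most about 0.2 points (for instance 9.3% becomes 9.1%). These are fixed-size calculations for the CAE30 test alone; they leave out the interim looks and the requirement that shortABx succeed first.

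**The case against.** The strongest reply is that (c) was written for exactly these patients. It sits beside (d), and protocol 4.1 asks for daily PCT only while a patient is eligible and on antibiotics, so someone whose PCT stopped under 6.2 complied with the protocol. Reading (d) literally would leave (c) with no effect for anyone who becomes ineligible while still on antibiotics. This stands as evidence of intent. It does not settle the matter: the conditions are listed jointly, and none is said to override another. The SAP's explanatory sentence after the list covers overruling criteria, under which recommendations continue, and not later exclusion criteria, for which 6.2 stops them.

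The discordance surveys in protocol Appendices F and G list abscess and empyema among the reasons for disagreement. This suggests that some such patients were expected still to be under stewardship review, and adds to the uncertainty about how they are handled.

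Two limits also stand. Only two component groups overlap. Death, septic shock, mechanical ventilation and readmission are not exclusion criteria, and need for ICU care and vasopressor use are overruling criteria. In addition, removal requires antibiotics to continue after the event.

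Finally, ITT keeps every one of these patients, SAP 4.7 examines each component, and the DMC receives component data by arm. The events therefore stay visible. But SAP 4.5 tests non-inferiority on PP, and neither document says what follows if ITT and PP disagree.

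**Conclusion.** Criteria (c) and (d) and protocol 6.2 conflict, and the conflict affects patients selected by their safety outcome. On the literal reading of (d), an event in either overlapping group, with antibiotics continuing, removes the patient from the set used for the CAE30 test.

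A reader might infer that CAE30 events in general remove patients from PP, or that removal is certain. The documents support neither: the direct overlap is two component groups, and (c) shows the opposite intent. Nor do they show that the 2.5% level is breached. Under the assumed rates (30% v 20%, 175 per arm), equal removal of up to 15% of events keeps the false non-inferiority rate at or below about 2.5%, and 2 v 1 points gives 2.2%. The level is passed with equal removal somewhat above 15%, or with a clear imbalance such as 3 v 1 points. Because component rates are not in the documents, the tables show a range and are not a forecast.

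This should be fixed before PP is derived.

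**What to change.** In SAP 3.1 and protocol 8.4, state that (d) and (e) are assessed only while the protocol requires PCT measurement: until the first of antibiotic stop, discharge, or PCT being stopped under protocol 1.6/6.2 because the patient met an exclusion criterion after enrolment. Criterion (e) needs the same limit because stewardship input ends at the same moment.

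Do not go further and protect patients from anything that happens on or after a first CAE30 event. That would excuse real deviations after shock or intubation, where the documents have PCT and recommendations continue.

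The cost is one sentence in each document and one derived stop date, with no change to patient management. CAE30 rates in PP may come out slightly less favourable.
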